### 9.3 Variables

The physician collects historical study-relevant data (demographic and clinical characteristics) from medical records if available (or else by interviewing the patient at the initial [baseline] visit) and treatment-related data during visits occurring within pre-defined data collection periods (see section 9.2.7). The physician documents the study-relevant data for each patient in the eCRF/EDC system. The CRF is kept as a stand-alone document (see Table 6) and is available upon request.

### 9.3.1 Variables to determine the primary endpoint

The variables for primary endpoint are:

- Annualized number of reported total bleeds.
- Severity of hemophilia.
- Severity of patient bleeding profile.
- Disease characteristics
- Prophylaxis regimen.
- Age.
- Previous exposure to damoctocog alfa pegol (i.e. naïve vs. non-naïve).

### 9.3.2 Variables to determine the secondary endpoints

The variables for secondary endpoints are:

- Safety:
  - Occurrence, duration, treatment, severity, and outcome of AEs, SAEs, and ARs (including AEs of special interest [hypersensitivity reactions, loss of drug effect, renal impairment, neurocognitive disorders, and inhibitor development]).
- Effectiveness:
  - Number of reported total, spontaneous, joint, and trauma bleeds.
  - Retrospective (diagnosed clinically, by imaging, by the patient, or by the physician) and prospective location and number of affected joints.
  - Joint health measured by HJHS.
  - Newly affected joints (number and location).
  - Reported bleeds (number, type, location) during study and up to 12 months prior to start of therapy with damoctocog alfa pegol. Prior bleeds to be estimated by the patient and the physician. Reported bleeds during the study will be recorded in the patient infusion diary and serious, life-threatening bleeds and surgery bleeds will be documented by the physician.
  - Number of infusions and FVIII consumption to achieve hemostasis during surgery.
  - Patient-report outcome:
    - Treatment satisfaction measured by Hemo-SAT A.
    - Health-related quality of life measure by Hemo-QoL (A and SF).
    - Work productivity and activity impairment measured by WPAI [+ CIQ: HS].

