
Population
	
Previously treated patients with hemophilia A receiving damoctocog alfa pegol with any kind of treatment modality (on-demand, prophylaxis, or intermittent prophylaxis), will be eligible to be enrolled into the study.

Variables
	
The variables for primary endpoint are:
 
 
• Annualized number of reported total bleeds.
 
• Severity of hemophilia
 
• Severity of patient bleeding profile
 
• Prophylaxis regimen
 
• Time on treatment (i.e., damoctocog alfa pegolnaive- or not)
 
• Disease characteristics
 
• Age.
 
 
The variables for secondary endpoints are:
 
 
• Occurrence, duration, treatment, severity, and outcome of AEs, SAEs, and ARs (including AEs of special interest [hypersensitivity reactions, loss of drug effect, renal impairment, neurocognitive disorders, and inhibitor development]).
 
• Number of reported total, spontaneous, joint, and trauma bleeds.
 
• Retrospective and prospective location and number of affected joints.
 
• Joint health measured by HJHS.
 
• Newly affected joints (number and location).
 
• Reported bleeds (number, type, location) during study and to 12 months prior to start of therapy with damoctocog alfa pegol.
 
• Number of infusions and FVIII consumption to achieve hemostasis during surgery
 
• Treatment satisfaction measured by Hemo-SAT A and Hemo-QoL (A and SF).
 
• Work productivity and activity impairment measured by WPAI [+ CIQ: HS].
 

Data sources
	
Historic data are based on medical records or on information provided by the patient during routine clinical visits. Treatment-related data are documented during visits that take place in routine practice. The patient documents bleeding events and all other events that require infusions in a patient infusion diary.
 
Validated patient questionnaires (Hemo-SAT A, Hemo-QoL [A and SF] and WPAI [+ CIQ: HS]) are used as sources for the

	
patient assessment on satisfaction and treatment adherence. The HJHS is used as source for joint health status. The HEAD-US score is used as source for joint health status of patients with hemophilic arthropathy.
								
Study size	The study aims to enroll at least 200 patients.								

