## 9. Research methods

### 9.1 Study design

This is a multinational, open-label, prospective, non-interventional, multicenter, cohort study of PTPs with hemophilia A receiving damoctocog alfa pegol with any kind of treatment modality (on-demand, prophylaxis, or intermittent prophylaxis). The study is planned to be conducted in multiple countries depending on timing of regulatory approval and national reimbursement access.

Prospective data will include prophylaxis regimen effectiveness measured by the number of ABR (reported in patient infusion diaries or documented by physicians, if patient infusion diary is not available), drug usage (IU/kg/infusion, IU/kg/year, and IU/kg/event), regimens used, patient-reported outcome (PRO) measurements (where applicable), such as validated, disease-specific and generic quality of life questionnaires and treatment satisfaction; as well as PK parameters (when available), joint outcomes (HJHS), and safety including AEs of special interest (hypersensitivity reactions, loss of drug effect, renal impairment, neurocognitive disorders, and inhibitor development) and drug-related ARs in standard clinical practice. Retrospective data will include documentation of previous therapy, lifetime duration on prophylaxis, medical condition, PK parameters (when available), and bleeds up to 12 months prior to use of damoctocog alfa pegol, in order to allow a stratification of patients by patient bleeding profile and disease characteristics (See Section 9.3.7).

Patients/legal representatives and physicians can choose from different prophylaxis regimens with damoctocog alfa pegol following approved local labels or any other regimen prescribed by the physician as part of normal clinical practice. Patients/legal representatives and physicians can choose to change the dosing regimen based on the patient's response to treatment at any time. A reason for the dose and/or frequency change should be documented.

The patients planned observation period will be 36 months (with the potential for further extension), for the collection of long-term safety data and continuous prospective monitoring of joint health status over time.

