### **9.1.2 Secondary endpoints**

The secondary endpoints are:

- Occurrence, duration, treatment, severity, and outcome of AEs of special interest (hypersensitivity reactions, loss of drug effect, renal impairment, neurocognitive disorders, and inhibitor development), AEs, SAEs, and ARs.
- Hemostasis during surgery measured by number of infusions and consumption of FVIII product
- Change in joint scores (HJHS) from baseline to 12 months, to 24 months, to 36 months.
- Joint status evaluation by ultrasound (HEAD-US score), if available or part of standard clinical practice.
- Number of affected joints by patient, and the change from baseline to 12 months, to 24 months and to 36 months.
- Annualized number of spontaneous, joint, and trauma bleeds.
- Number of reported bleeds (total, spontaneous, joint, and trauma) during the study compared with number of reported bleeds (total, spontaneous, joint, and trauma) for previous FVIII products in the 12 months prior to enrollment into the study.
- Proportion of patients with 0 bleeds, and the difference in proportion comparing to previous prophylaxis treatment.
- Description of PK parameters for previous FVIII products versus damoctocog alfa pegol (if available in routine clinical practice).
- Efficacy of treatment of break-through bleeds.
- Change from baseline to 12 months, to 24 months and to 36 months in treatment satisfaction (Hemo-SAT A score).
- Change from baseline to 12 months, to 24 months and to 36 months in treatment satisfaction (Hemo-QoL [A and SF] score).

- Change from baseline to 12 months, to 24 months and to 36 months in work productivity and activity impairment (WPAI score).

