### **Sub-populations:**

Data will be stratified by prophylaxis dosing regimen (following approved local label, see Section 9.7.3), severity of hemophilia (mild, moderate, or severe), severity of patient bleeding profile at baseline (ABR in the last 12 months prior to enrollment), medical history (in particular joint status [affected joint: yes/no; 1 affected joint/>1 affected joint]), age groups, and time on treatment (i.e., damoctocog alfa pegol-naive or not). The prophylaxis-dosing regimen as prescribed by the physician at the beginning of the study will be used for stratification, unless otherwise stated.

Assignment of patients into treatment categories in case of changes to the regimen or switch to on-demand will be specified within SAP. Whenever reasonable, further subgroups (e.g., sex, baseline patient/disease/pre-treatment characteristics) will be specified in the SAP. Selected tables (including safety events, treatment administration and prophylaxis regimen) will be presented by history of inhibitors and exposure days (to FVIII product) at baseline.

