#### **ABR:**

Summary statistics of the number, type, location, and severity of reported bleeds (total, spontaneous, joint, and trauma) will be presented.

The primary analysis on ABR will be performed in patients receiving prophylactic treatment. ABRs will first be characterized using descriptive statistics by calculating mean ( $\pm$  standard deviation [SD]), median, minimum, and maximum. Further, the mean ABRs along with 95% CIs will be estimated using a negative binomial regression model corrected for over-dispersion, and with relevant treatment and disease characteristics as covariates and observed prophylactic treatment period as an offset variable.

When enough data is collected, additional analyses include: 1) comparing the ABR in patients receiving prophylactic treatment with those who are not treated with standard prophylaxis; 2) comparing the ABR in patients receiving damoctocog alfa pegol prophylactic treatment with the ABR prior to the damoctocog alfa pegol treatment.

Further details of the analysis will be described in the SAP.

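### Section 9.3.2 has prior bleeds estimated where 9.3 and 9.4 put medical records first, and the source is not recorded, so a difference in capture can enter the before/after bleed comparisons

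*Protocol*

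**What the plan says.** **Source of the prior count.** Section 9.3 says that the physician collects historical data "from medical records if available (or else by interviewing the patient at the initial [baseline] visit"; section 9.4 repeats that order. The abstract gives no order: "Historic data are based on medical records or on information provided by the patient during routine clinical visits". Section 9.3.2, which deals with this variable specifically, says: "Prior bleeds to be estimated by the patient and the physician". Section 9.3.4 lists the number, type and location of earlier bleeds, to be documented if available. It does not list where the count came from.

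**Source of the on-study count.** Section 9.3.2 continues: "Reported bleeds during the study will be recorded in the patient infusion diary", with the physician documenting serious, life-threatening and surgery bleeds. Section 9.1 describes on-study bleeds as "reported in patient infusion diaries or documented by physicians, if patient infusion diary is not available". A footnote to Table 3 adds that the physician asks about bleeds at each visit.

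**Where the two counts meet.** A secondary endpoint in 9.1.2 sets on-study bleeds against those "for previous FVIII products in the 12 months prior to enrollment into the study". Another takes the difference in the proportion of bleed-free patients against previous prophylaxis. Section 9.7.4 adds, once enough data are available, an analysis "comparing the ABR in patients receiving damoctocog alfa pegol prophylactic treatment with the ABR prior to the damoctocog alfa pegol treatment". Section 9.7.1 also stratifies by "severity of patient bleeding profile at baseline (ABR in the last 12 months prior to enrollment".

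**The concern.** A before/after comparison within patients assumes that a bleed had the same chance of being counted in both periods. Here the first period may rest on an estimate made at entry and the second mainly on prospective recording. If the two capture different fractions of the true bleeds, the gap appears in the difference and looks like a change under treatment. A larger sample narrows the interval around that wrong value but does not remove the error.

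The conflicting rules make this worse. A site that follows 9.3.2 as written may use an estimate even when records exist; a site that follows 9.3 would not. Unless the source is noted when the count is entered, no later analysis can separate documented from recalled values. At stake are the secondary before/after results and, to a lesser degree, correct assignment of patients to the bleeding-profile strata.

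**Working it through.** **1. The text.**

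| Section | Rule for prior data | Records first? |
|---|---|---|
| 9.3 and 9.4 | Records; interview only if records are unavailable | Yes |
| Abstract | Records or patient information | No order given |
| 9.3.2 (prior bleeds) | Estimate by patient and physician | Records not mentioned |

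No section says which rule governs the prior bleed count.

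**2. Size of a possible error.** The protocol gives no figure for the accuracy of the prior count, so there is none to reproduce, and every error size below is an assumption.

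Inputs:
- from section 9.5: ABR 4 and dispersion 1 (the figures it cites from the earlier trial on prophylaxis) and n = 180 (200 × 0.9);
- from 9.1 and 9.3.4: 36 months of observation and a 12-month prior window;
- assumed: no true change, complete on-study capture, full follow-up, and one factor f (recorded prior bleeds divided by true prior bleeds) for every patient.

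Let a patient's true rate λ have mean μ = 4 and variance μ² = 16 (dispersion 1). The prior count is Poisson with mean fλ over one year. The on-study rate is a Poisson count with mean 3λ, divided by 3.

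- Expected on-study minus prior difference: μ(1 − f).
- Variance per patient: μf + μ/3 + μ²(1 − f)² = 4f + 4/3 + 16(1 − f)².
- SE = √(variance/180).

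| f | Difference per year | Variance | SE | Difference/SE |
|---|---|---|---|---|
| 0.8 | +0.8 | 3.2 + 1.333 + 0.64 = 5.173 | 0.170 | 4.7 |
| 1.2 | −0.8 | 4.8 + 1.333 + 0.64 = 6.773 | 0.194 | 4.1 |
| 1.3 | −1.2 | 5.2 + 1.333 + 1.44 = 7.973 | 0.210 | 5.7 |

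A simulation of the same model (3000 runs) gave SEs of 0.17, 0.19 and 0.21.

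If only a share p of the counts carries the error, the shift is pμ(1 − f). With p = 0.5 and f = 0.8 or 1.2 it is 0.5 × 0.8 = 0.4 bleeds per year.

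**3. A second setting.** Take the planning mean of 6 from section 9.5, one year in each period, and let d be the completeness of on-study capture and r that of the prior count. With no true change, the apparent on-study/prior ratio is d/r and the difference is 6(d − r).

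- With d = 1, r from 0.7 to 1.5 gives ratios from 1.43 to 0.67 and differences from +1.8 to −3.0.
- In a paired simulation with d = 1, the 95% interval for the change excluded zero in about 5% of studies at r = 1, in 61 to 66% at a 10% error, and in over 99% at r = 0.8 or 1.25.
- With d = 0.8 and r = 1 the ratio is 0.80: diary omission alone makes bleeding look lower.
- With d = r = 0.8 the ratio is 1.00: equal under-capture cancels.

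**The case against.** The strongest reply is that 9.3 states a default and 9.3.2 only says who produces the figure. The physician holds the records, so an estimate may draw on them. That reading is possible, but 9.3.2 does not require it, and sites may act differently.

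Several other points stand and limit the concern:

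- On-study bleeds are not taken from the diary alone. Physician documentation and questions at visits contribute, so recall can enter both periods and partly cancel.
- Section 9.9 already names information and reporting bias, limited historical data and unstandardised diaries. Only the change of source between periods is not named.
- The CRF is a separate document that is not shown. It may already hold a source field; the protocol merely does not ask for one.
- The study is descriptive. The before/after endpoints are secondary, and the ABR comparison is conditional on enough data.
- The strata in 9.7.1 use 12 months before enrollment, whereas 9.3.2 and 9.3.4 count back from the start of therapy. For patients already on the drug these windows differ, so the stratifying count need not be the count collected under 9.3.2.
- Analysis detail belongs in the SAP. The source rule and the recording of the source, however, are data-collection matters that must be settled at entry.

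A reader might infer that the before/after comparison will show a false benefit, or that the primary ABR is biased. The documents support neither. They give no size or direction for the error: over-recall flatters the product, under-recall counts against it, and diary omission flatters it. The overall on-treatment ABR does not use the prior count.

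**Conclusion.** The point holds in a limited form. The protocol gives two unreconciled rules for the source of the prior bleed count and does not ask for the source to be recorded. That count is then compared with bleeds captured by a mainly prospective method. Any difference in capture goes directly into the secondary before/after bleed endpoints and the conditional ABR comparison.

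Under the assumptions shown, a uniform 20% error gives a spurious change of about 0.8 bleeds per year at a true ABR of 4, or 4 to 5 standard errors. The shift is proportionally smaller if some counts come from records, and zero if both periods under-capture equally. These figures show sensitivity and do not predict what will happen. The overall single-arm ABR is unaffected; error in the prior count can also misclassify patients in the bleeding-profile strata. This is a worthwhile, inexpensive improvement and not a threat to the main result.

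**What to change.** - Align 9.3.2 with 9.3 and 9.4: take the prior count from records or an earlier diary where these exist, and estimate it only otherwise.
- Require the source (documented or estimated) to be recorded for each patient when the count is entered, unless the CRF already does so.
- Keep all patients in the main before/after comparison, and repeat it in those with a documented prior count as a sensitivity analysis.

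The cost is one data field, a sentence in 9.3.2 and a little more analysis. The sensitivity set will be smaller and may be selected by quality of record-keeping. That is why it should support the all-patient comparison and not replace it.

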### 9.3.3 Demography

For demographic/socio-demographic assessment, the following data will be recorded:

- Year of birth.

- Age.
- Sex.
- Race (e.g., Asian, Black, White, not reported) (only where legally permitted).
- Ethnic origin (e.g., not Hispanic or Latino, Hispanic or Latino, not reported) (only where legally permitted).
- Body weight, height, body mass index, and vital signs (routine assessments only).

### 9.3.4 Hemophilia Disease history

Disease history describes any medical findings that are relevant to the underlying disease and were present before enrollment into the study. Findings and diagnoses meeting the criteria listed below have to be documented, if available:

- Date of diagnosis (at least the year).
- Type of gene mutation, if available.
- Family history of hemophilia.
- Family history of inhibitors.
- Severity of hemophilia at initial diagnosis.
- Age/age group at first treatment with factor FVIII replacement therapy.
- Age at initiation of prophylaxis therapy, if applicable.
- Duration of prophylaxis treatment lifetime.
- Patient history of inhibitors (date, high/low titer, etc.).
- ITI history.
- Most recent FVIII product (name, treatment modality [on-demand, prophylaxis, or intermittent prophylaxis], dose/regimen) up to 12 months prior to start of therapy with damoctocog alfa pegol.
- PK parameters from most recent FVIII products, if available.
- Number and location of affected joints.
- Reported previous bleeds (number, type, and location) within 12 months prior to start of therapy with damoctocog alfa pegol.
- Ultrasound scanning (Hemophilia Early Arthropathy Detection with Ultrasound [HEAD-US]) to evaluate joints of patients with hemophilic arthropathy [28].

### 9.3.5 Co-morbidity (medical history and concomitant diseases)

Co-morbidities are any medical findings, as they pertain to the study indication, that were present up to 12 months prior to start of therapy with damoctocog alfa pegol, independent of whether or not they are still present. They have to be documented under medical history/concomitant diseases, if available.

Findings meeting the criteria listed below are considered to be relevant to the study indication and have to be documented, if available:

- Human immunodeficiency virus.
- Hepatitis C virus (full serology).
- Hepatitis B virus (full serology).
- Liver disease.
- Hypertension.
- Chronic arthropathy (i.e., not hemophilic arthropathy).
- Chronic pain.
- Renal disease.
- Neurocognitive disorders.
- Neurological disorders.
- Previous hypersensitivity to FVIII administration.

### **9.3.6 Prior and concomitant medication/treatments**

Medication taken /treatment received prior to study start (initiated and stopped before study start) is termed prior medication/treatment. Prior medication/treatment for hemophilia A at inclusion (on-demand, prophylaxis, or intermittent prophylaxis) received up to 12 months prior to study enrollment or initiation of damoctocog alfa pegol, whichever comes earlier are considered to be relevant to the study indication and have to be documented, if available.

All medication taken/treatment received (either initiated before study start or during the study) in addition to damoctocog alfa pegol for any indication is termed concomitant medication/treatment and has to be documented, if available.

### **9.3.7 Exposure/treatment**

During the study, damoctocog alfa pegol exposure/treatment data will be collected by the physician, including but not limited to:

- Date of first and last dose during the study.
- Exposure days previous treatment.
- Damoctocog alfa pegol exposure days.
- Date of damoctocog alfa pegol treatment start.
- Date of first and last dose before enrollment (if applicable).
- Prescribed dose of damoctocog alfa pegol.
- Prescribed regimen of damoctocog alfa pegol.
- Reason for any dose and/or regimen change
- Number of infusions and by-product FVIII consumption (for overall, prophylaxis, bleeds, and other events)
- Reason for selection of dose/regimen at baseline (first visit). Physician to choose and rank in order of importance the top 3 reasons from predefined list (see Annex 3).

- PK parameters from damoctocog alfa pegol (Half-life [ $t_{1/2}$ ], FVIII trough, FVIII peak levels, in-vivo recovery), if available.
- Any surgery requiring an infusion, is also documented, including the following information:
  - Date of treatment.
  - Type of surgery (major or minor; see Annex 4), if applicable.
  - Number of infusions.
  - Dose (IU) per infusion/bolus infusion/other for each event/surgery (if applicable).
  - Total bleeding volume (mL) during surgery.
  - Blood transfusions (red blood cells, platelets, etc.) and total volume (mL).

For data collected by the patient/legal representative (where applicable), a diary will be used as source:

- Patient infusion diary. All bleeding events are documented, including:
  - Date of bleeding event.
  - All data referent to prophylaxis infusions.
  - Reason for infusion and location of bleed.
  - Date of treatment.
  - Number of infusions and dose per infusion for each bleeding event.

